Statistic analysis	For the evaluation of the primary endpoint patients will be dichotomized by the presence or absence of the sealant reinforcement. Further, patients will be categorized by the type of pancreatic fistula rate defined according to the International Study Group of Pancreatic Fistula (ISGPF). Next, a contingency table will be created to calculate positive predictive value, specificity, sensitivity, and c-index. Association between sealant reinforcement and POPF rate will be expressed as odds ratio calculated by logistic regression models with the appropriate covariates. The strength of association between categorical variables will be tested with a chi-square test with Yate's correction. Secondary end points will be analyzed descriptively by tabulation. Chi-square tests will be used to test associations among categorical variables, while Student's t-test or Mann-Whitney U-test will be used to compare continuous normal or non-normal data, respectively. Time dependent variables will be tested by Kaplan-Meier analysis and Cox regression. Statistical analysis will be performed with R.
Sample size	64 patients, 32 in each group
Ethical approval	This study is approved by the Clinical Research Ethics Committee of Aragon (CEICA)
Duration of the study	The study will begin on February 1, 2018. It is estimated a duration of 1.5 years, according to the PD rate of our center (40-50 year). Estimated end date: July 31, 2019.
Participating centers	Division of Hepato-Pancreato-Biliary Surgery, Department of Surgery, Miguel Servet University Hospital

2. PATIENT VISIT AND EVALUATION.

There will be a first visit in an outpatient clinic where the patient will be informed about the study in detail and will be offered to participate in it as long as it meets the selection criteria. Two copies of the informed consent will be signed, one of them for the patient and the other will be kept together with the study documentation. A first evaluation of the patient will be carried out as it appears in the data collection notebook.

3. STRUCTURE OF THE ORGANIZATION.

3.1. Sponsor.

Investigator Initiated Research Grant from Baxter S.L., Chicago, Illinois, United States, convened on March 24, 2017.

3.2. Principal investigators.

Principal investigator:

[name], FACS
Associate Professor at University of Zaragoza
Attending Surgeon in General Surgery
Division of Hepato-Pancreato-Biliary Surgery
Miguel Servet University Hospital
[name]

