All patients undergoing PD, either by laparotomy or laparoscopy, are potential participants. Their diagnoses include chronic pancreatitis, benign (for example, cystadenoma) or malignant tumors (adenocarcinoma, NET, metastasis, etc.). They will be invited to participate in the study and will be informed of the possible advantages and disadvantages. The randomization process will begin for any patient who agrees to participate after informed consent.

7.3. Inclusion and exclusion criteria.

Inclusion criteria: patients submitted to PD by laparoscopic or open approach for benign / malignant tumor or chronic pancreatitis; ASA < 4; men and women ≥ 18 and ≤ 80 years of age.

Exclusion criteria: patients under 18 and over 80 years old; ASA score ≥ 4 ; subjected to multivisceral resections different from PD; patients with acute necrotizing pancreatitis; immunosuppressed patients; patients who have not signed the informed consent; patient with a contraindication to PD.

7.4. Intervention techniques and materials.

The indications for performing a PD are multiple. The type of reconstruction to be performed will depend basically on the characteristics of the pancreatic remnant. However, in our center, the usual reconstruction technique is the duct-to-mucosa type pancreaticojejunostomy.

Depending on the randomization, patients will be operated as follows:

- 1) Basic treatment: standard duct-to-mucosa pancreaticojejunostomy.
- 2) Basic treatment plus Hemopatch: standard pancreaticojejunostomy + reinforcement with 2 Hemopatch of 90 x 45 mm, one on each side (lower and upper) as a "scarf".

In both groups, passive external drainage is mandatory for a period of 7 days with drainage placed next to the anastomosis but not in contact with it. The drain can be a Penrose drain, a Jackson-Pratt drain or Blake without active suction. Suction drains are not allowed.

Adjvant procedures

Wrapping, sealing with fibrin or serous patch with another adjacent organ are not acceptable. No resection of adjacent hollow organ is allowed (excepting those included in the standard DPC).

Materials

Hemopatch is a hemostatic-sealant made of collagen that resorbs in 6-8 weeks. The active side is covered with a polyethylene glycol film for better adhesion.

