All patient data are anonymous. Each patient who meets the selection criteria and has signed the informed consent will be entered into a database and identified by a number (from 1 to 64). The list of patient identification numbers will be in the hands of the principal investigator. After carrying out the surgery, the patient number is entered into an online computerized randomization tool ("Randomizer for clinical trials"), <https://www.meduniwien.ac.at/randomizer>. It is a tool of the University of Vienna in Austria, where the study is registered, which allows, once the patient number is entered, the randomization of the same, obtaining one of the two methods to compare, as explained in Section 7.4. (32 patients in each study group):

- Basic treatment: duct-to-mucosa pancreaticojejunostomy WITHOUT Hemopatch reinforcement.
- The same, but reinforced WITH Hemopatch.

Once the treatment to be performed is obtained, surgery will be carried out according to the treatment obtained in the randomization.

8.3. Efficacy assessments (that is, data that must be collected).

- Daily drainage debit.
- Concentration of amylase and lipase from the drainage fluid (days 3, 5 and 7 postoperatively) and every 2 days in case of permanent fistula.
- Number of postoperative days with drainage (minimum 7 days). If the amylase / lipase content of the drainage on the 7th postoperative day is within normal limits, it may be withdrawn.
- Body temperature, VAS pain score, leukocyte count and CRP.
- Duration of the stay in the ICU.
- Duration of the total hospital stay.
- Reinterventions, including percutaneous drainage of collections.
- Re-entry.
- Degree of complications according to the Clavien-Dindo classification, including both complications derived from surgery (delay of gastric emptying, bleeding, biliary fistula, wound infection, intra-abdominal

abscess, etc.) and general (atelectasis, pneumonia, urine infection, thromboembolism, etc.)

8.4. Patient data sheet.

It contains patient information including personal history (ie, smoking, diabetes, BMI), preoperative and postoperative data, intraoperative incidents, special treatment details, complications and adverse events such as new onset diabetes, pneumonia or heart problems.

All the data are collected in a central database.

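### Section 8.2 gives two opposite orders for surgery and randomisation, and no section fixes the moment of allocation

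*Combined protocol and SAP*

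**What the plan says.** Section 8.2 (Randomization and groups) contains both timing statements. The first is "After carrying out the surgery, the patient number is entered into an online computerized randomization tool". The last sentence of the section is "Once the treatment to be performed is obtained, surgery will be carried out according to the treatment obtained in the randomization".

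The same section says that anyone eligible who "has signed the informed consent will be entered into a database and identified by a number (from 1 to 64". That range equals the full sample, given there as "32 patients in each study group". Section 8.2 does not say on which day the number is issued.

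Four other places bear on timing:

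- Section 2 describes "There will be a first visit in an outpatient clinic where the patient will be informed about the study in detail", and continues "Two copies of the informed consent will be signed". Consent is therefore described at an outpatient visit, before the operation.
- Section 7.2 says "The randomization process will begin for any patient who agrees to participate after informed consent".
- Section 7.4 makes the operation depend on the randomised arm. The arms are a standard duct-to-mucosa pancreaticojejunostomy, alone or reinforced with two patches.
- Section 7.7 lists an operation not performed because of unresectability among the reasons for withdrawing a patient. Section 7.3 excludes multivisceral resections other than PD.

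**The concern.** The allocated treatment is applied during the operation, so it cannot be assigned once the operation is over. Staff who follow section 8.2 as written have no rule they can carry out, and each theatre team would have to choose its own moment.

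The choice matters in two ways.

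- **Who is randomised.** Unresectability, or the need for an excluded multivisceral resection, may become apparent only at operation. If allocation has already been made, such a patient is randomised but does not receive the study procedure as planned. Section 8.5 defines no analysis set, so the plan does not say how that patient would be counted.
- **What the surgeon knows, and when.** The surgeon must know the arm once the patch is or is not applied, and section 6.1 claims blinding only for the patient and the outcome observer. Earlier knowledge is a different matter. A surgeon who knows the arm while building the anastomosis could, even unintentionally, build it differently, and the primary endpoint depends on that anastomosis.

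**Working it through.** The point concerns the order of events, so the main check is to test each possible allocation moment against the text.

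| Allocation moment | 8.2, first statement | 8.2, last sentence | 7.2 | 7.4 | Unresectable patient may already be randomised | Arm may be known during anastomosis |
|---|---|---|---|---|---|---|
| After consent, before the operation | conflicts | fits | fits | fits | yes | yes |
| In theatre, after resection, before anastomosis | fits only if surgery means the resection | fits only if surgery means the rest of the operation | fits | fits | no | yes |
| In theatre, after anastomosis, before the patch | fits only if surgery means the resection and anastomosis | fits only if surgery means the patch step | fits | fits | no | no |
| After the operation has ended | fits | conflicts | fits | conflicts | no | no, but the patch cannot be delivered |

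No row satisfies both statements of section 8.2 literally. The two middle rows satisfy them only if the word surgery means one part of the operation in the first statement and a later part in the last. Section 7.2 fits every row, because it says only that the process starts after consent. Section 7.4 excludes only the last row. Neither section selects a moment.

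**What one patient represents.** The inputs are 32 per group (section 8.2), and 57 patients raised to 64 for 10% expected losses (section 8.1).

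- The plan's inflation reproduces: 57 / (1 − 0.10) = 63.3, rounded up to 64.
- Loss allowance: 64 − 57 = 7 patients in total.
- One patient randomised and then withdrawn: 1 / 32 = 3.1% of an arm, or 1 / 7 = 14% of the allowance if the allowance is meant to cover such patients. Section 8.1 does not say which losses it covers.

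The figures 57 and 64 are used here only as the plan states them; whether 57 is the right number is a separate question. The documents give no rate of unresectability at operation or of excluded resections found at operation, so the expected number of affected patients cannot be calculated.

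**Recruitment time.** The synopsis says "It is estimated a duration of 1.5 years, according to the PD rate of our center (40-50 year".

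- PDs expected in 1.5 years: 1.5 × 40 = 60 to 1.5 × 50 = 75, against 64 to be randomised.
- Mean interval between PDs: 365 / 50 = 7.3 days to 365 / 40 = 9.1 days.

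The interval is an added cost of the fix only for a patient who would otherwise have filled one of the 64 places and is replaced by a later PD. It also assumes that every PD enters the trial.

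**The case against.** The strongest reply is that this is loose wording, perhaps from translation. The patch is an addition to an otherwise identical operation, and section 7.4 has patients operated according to their arm, so randomising after the operation ends is already ruled out by the protocol. The only statement that places entry in the tool relative to surgery puts it late. Under a sensible late reading, the trial would already do roughly what is asked here. Withdrawal for unresectability would also mainly cost numbers, since resectability is judged before any patch is applied and some losses are budgeted.

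Much of this stands, and it limits what may be inferred:

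- A reader might infer that the trial will randomise after the operation and so cannot deliver its treatment. The documents do not support that; they show a rule that cannot be followed literally.
- A reader might infer early allocation from the numbers 1 to 64. Section 8.2 describes an identification number, and allocation happens only when it is entered in the tool. A number issued early does not by itself mean an arm assigned early.
- A reader might take patients needing a multivisceral resection to be withdrawn under section 7.7. That section does not list them; the resection is an exclusion criterion in section 7.3.
- A reader might infer that a change of reconstruction could break the comparison. Section 7.4 does let reconstruction depend on the pancreatic remnant, but duct-to-mucosa is the centre's usual technique, and the synopsis and section 8.2 specify it for both arms.

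What does not stand is that the sensible reading can be left implicit. Section 8.2 uses the same word for what comes before allocation and for what comes after it, and nothing else tells staff when to open the tool.

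**Conclusion.** The point holds as a wrong rule in section 8.2: the two statements give opposite orders, and the first, read literally, cannot deliver an intraoperative patch. Confidence in the textual conflict is high.

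The consequences are conditional on allocation being made early in practice, which the documents neither state nor exclude. They do not show selection bias, performance bias or a failure of the blinding claimed in section 6.1. The total effect is not quantifiable from the documents; the per-patient figures above are only a scale for it. The point should be fixed before recruitment, because randomisation is the basis of the comparison and the remedy costs almost nothing.

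**What to change.** Replace the first timing statement in section 8.2 and align sections 7.2 and 7.4 with it, so that one moment is stated everywhere: the number is entered in the online tool in the operating room, after resectability and eligibility (including absence of an excluded resection) are confirmed, and immediately before the patch would be applied. Preferably this comes after the duct-to-mucosa anastomosis is complete. Allocation after confirmed resectability but before the anastomosis would also remove the contradiction, but it would leave the surgeon able to know the arm while building the anastomosis.

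Keep the identification number given at consent separate from the randomisation sequence of 64. Log consented patients who do not reach allocation as not randomised, with the reason, and align section 7.7 so that unresectability found before allocation is a reason for not being randomised.

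The cost is protocol wording, a few minutes in theatre with the existing tool, and somewhat more consents than randomised patients; the documents do not show how many more. Where a patient would otherwise have taken one of the 64 places, replacement adds about 7 to 9 days. The planned 1.5 years is already tight at the lower PD rate (60 PDs for 64 places), with or without this change.

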Objetives	Primary objective: 
• To demonstrate the effectiveness of Hemopatch in the prevention of postoperative pancreatic fistula after PD with duct-to-mucosa reconstruction against ductomucosal reconstruction without Hemopatch Secondary objectives: 
• To assess the safety and tolerance of Hemopatch in patients undergoing PD
Interventions	Performing duct-to-mucosa anastomosis with or without Hemopatch reinforcement after PD
Inclusion and exclusion criteria	Inclusion criteria: patients submitted to PD by laparoscopic or open approach for benign / malignant tumors or chronic pancreatitis; ASA < 4; men and women ≥ 18 and ≤ 80 years of age. Exclusion criteria: patients under 18 and over 80 years old; ASA score ≥ 4 ; subjected to multivisceral resections different from PD; patients with acute necrotizing pancreatitis; immunosuppressed patients; patients who have not signed the informed consent; patient with contraindication of PD performance
Results	Primary point: Type B and C postoperative pancreatic fistula defined according to the criteria of the International Study Group on Pancreatic Fistula (ISGPF) Secondary endpoints: 
1) Duration of postoperative hospital stay.2) Length of stay in intensive care unit.3) Measurement of drainage debit.4) Reinterventions including interventional radiology.5) Infection of the surgical site and / or dehiscence of the

Study protocol - Use of Hemopatch as a sealant in pancreaticojejunostomy after PD.
Version 2.0.

	wound; complications in the deep organ space up to 30 days postoperatively. 6) Delayed gastric emptying. 7) Biliary fistula. 8) Postoperative hemorrhage. 9) Death, regardless of the cause.
Type of study	Prospective randomized double blind unicentric clinical trial

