Results. Postoperative complication rates were (with NHS-PEG patch/without NHS-PEG patch): pancreatic fistula (A: 7.7%/7.7%; B: 0%/7.7%; C: 0%/15.5%); biliary fistula: 7.7%/15.4%; DGE: 7.7%/7.7%; hemorrhage: 7.7%/15.5%; exitus: 0%/7.7%; readmission: 7.7%/46%; mean stay: 21.3/26.1 days; other complications: 61.5%/46.2%.

Discussion. Sealing with NHS-PEG patch to prevent postoperative pancreatic fistula after DTM pancreaticojejunostomy can offer a new possibility to decrease POPF, with less fistula rate B and C, less hospital stay an less healthcare costs. Randomized controlled trials with larger number of patients should be performed to support this theory.

Therefore, we have design the following randomized controlled trial in order to validate our positive experience with Hemopatch in PD.

5. HYPOTHESIS / OBJECTIVE.

This unicentric, double-blind, randomized study investigates the efficacy and tolerance of Hemopatch in the prevention of POPF type B and C after a PD. The goal for Hemopatch is to reduce the risk of POPF type B and C from 30% to 15%.

6. STUDY DESIGN.

6.1. Type of study.

Unicentric, randomized, controlled, double-blind, prospective study with a parallel design of two groups. After giving informed consent, patients will not know to which group they have been assigned (reinforcement with Hemopatch or not). After the last follow-up visit on postoperative day 30, the patients can receive this information if they wish.

This study is also blind on the part of the observer; the final result will be determined by an independent observer, making this a double-blind study.

6.2. Primary objective and secondary objectives.

Primary endpoint: POPF type B and C, according to the definition of the ISGPF (Bassi, Surgery 2005), that is, the secretion of pancreatic fluid externalized through a drain or removed during a reoperation, independently of the color and / or appearance on day 3 or later, whose amylase is 3 times the values of serum amylase or collections (infected or not) detected by fistulography or other imaging techniques (computed tomography, ultrasound, magnetic resonance imaging). See attached table.

Grade	A	B	C
Clinical conditions	Well	Often well	Ill appearing / bad
Specific treatment*	No	Yes / no	Yes
US / CT (if obtained)	Negative	Negative / positive	Positive
Persistent drainage (after 3 weeks)**	No	Usually yes	Yes
Reoperation	No	No	Yes
Death related to POPF	No	No	Possibly yes
Signs of infections	No	Yes	Yes
Sepsis	No	No	Yes

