Readmission	No	Yes / no	Yes / no

US, Ultrasonography; CT, computed tomographic scan; POPF, postoperative pancreatic fistula.
*Partial (peripheral) or total parenteral nutrition, antibiotics, enteral nutrition, somatostatin analogue and/or minimal invasive drainage.
**With or without a drain in situ

Secondary endpoints:

- 1) Duration of postoperative hospital stay.
- 2) Duration of stay in intensive care unit.
- 3) Measurement of drainage debit.
- 4) Reinterventions including interventional radiology
- 5) Infection of the surgical site and / or dehiscence of the wound; complications in the deep organ space up to 30 days postoperatively.
- 6) Delayed gastric emptying.
- 7) Biliary fistula.
- 8) Postoperative hemorrhage.
- 9) Death, regardless of the cause.

6.3. Duration of the study.

The study will begin on February 1, 2018. Patients will be recruited at Miguel Servet University Hospital from January 1, 2018 to July 31, 2019. All patients randomly assigned will be followed for 30 days after surgery, or during the total stay in case it is longer than 30 days. They will also be evaluated in external consultations in the postoperative period for 3 months. A period of 4-6 months is considered to evaluate the data and the study will entail 2 years in total.

7. PATIENTS.

7.1. Criteria.

Despite improvements in morbidity after pancreatic resection, POPF after PD remains problematic. The incidence varies markedly in the literature, ranging from 0% to 64%, and 35% are clinically relevant. This great variability is attributed in part to the

indication and extension of the resection, as well as to the comorbidities of the patient. Other factors, such as age, male sex, obesity, prolonged operation time and a soft pancreas, as well as multivisceral resections increase the risk of fistula. The sequelae of pancreatic fistula after PD cover a broad spectrum. These patients often require visits to the emergency department, hospital readmissions, percutaneous drainage guided by interventional radiology, prolonged parenteral antibiotic therapy, radiological surveillance and numerous postoperative visits. The complications derived from the fistula double the cost of hospital treatment and dramatically increase the use of health resources.

7.2. Recruitment.

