- **Grade A:** clinically asymptomatic patient, persistent fistula, absence of intra-abdominal fluid collection in imaging test. No therapeutic consequence; the hospitalization is not prolonged.
- **Grade B:** symptomatic patient, requires diagnostic evaluation and therapeutic management. Clinically stable patient, may complain of abdominal pain, fever, nausea and intolerance to oral intake. Normally there is a collection of at least 3 x 3 cm in image tests. Therapeutic consequences: you must start antibiotic treatment and absolute diet. Invasive intervention (percutaneous drainage) may be necessary; hospitalization usually lasts.
- **Grade C:** clinically unstable patient (sepsis). Therapeutic consequences: it requires intensive care, percutaneous drainage or reoperation if the drainage has been removed or is not properly positioned. Hemorrhage is frequent; high expected mortality.

The objective of this study is to evaluate the rate of type B and C fistulas after pancreatic resection with and without Hemopatch.

7.7. Termination conditions / Adverse events / Suspected unexpected serious adverse reaction.

Criteria for withdrawing a patient from the study:

- Patient's desire to be removed from the study.
- Intervention not performed (due to unresectability).

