- The investigator suspects a serious threat to the patient's well-being. Adverse events (any sign or symptom that affects the patient's well-being) and serious adverse events (life-threatening, prolongs hospital stay, results in persistent disability or leads to death during the observation period), as cardiopulmonary problems, in the gastrointestinal tract, anaphylactic shock or embolism will be recorded through daily postoperative visits until discharge and during the final visit on the 30th postoperative day. All adverse effects of clinical relevance and all serious adverse effects will be recorded in the case report form along with the degree of the complication (according to the Clavien-Dindo classification). The principal investigator must be informed within 24 hours about the serious adverse effects that occur during the hospital stay. The presence of a causal relationship between adverse effect or serious adverse effect and the intervention of the trial will be judged by the investigator. Serious adverse effects will be reported immediately (ie, within 5 days after recognition) by all investigators to the coordinating investigator. The coordinating researcher must inform the responsible ethics committee and the research sponsor. A list of all serious adverse effects must be compiled.

8. DATA.

8.1. Calculation of the sample size.

The sample size was calculated by comparing two proportions, with a level of statistical significance of 5% (alpha) and a statistical power of 80% (1-beta), and taking into account the preliminary data obtained regarding the rate of POPF in the two groups: 23% for the control group, and 7% for the Hemopatch group.

With these assumptions, it will take 57 patients to detect, with an 80% probability and a level of significance of 5%, a decrease of the POPF rate of 23% in the control group to 7% in the experimental group (Hemopatch). Considering an expected proportion of losses of 10%, the sample size will be 64 patients.

8.2. Randomization and groups.

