All study personnel must sign a confidentiality agreement that covers all aspects of the study and its data. The study directors will take particular responsibility for the security of the data, the documents of origin and the information about the patients.

The coordinator of the main study is also responsible for continuing education in Good Clinical Practices (GCP) in accordance with the Declaration of Helsinki.

8.5. Statistical methods and data analysis.

For the evaluation of the primary objective, patients will be dichotomized by the presence or absence of the sealant reinforcement. In addition, patients will be classified by the type of pancreatic fistula defined according to the ISGPF. Next, a contingency table will be created to calculate the positive predictive value, specificity, sensitivity and the c-index. The association between sealant reinforcement and pancreatic fistula rate will be expressed as an odds ratio calculated by logistic regression models with the appropriate covariates. The strength of association between the categorical variables will be tested with a chi-square test with the Yate correction.

Secondary objectives will be analyzed descriptively by tabulation. Chi-square tests will be used to test associations between categorical variables, while Student's t-test or Mann-Whitney U-test will be used to compare normal or non-normal data, respectively. Time-dependent variables will be tested by Kaplan-Meier analysis and Cox regression. The statistical analysis will be carried out with R.

9. PATIENT SAFETY.

A monitoring team will receive all patient data electronically including expected and unexpected events and side effects for all patients in the study. All patient data are analyzed to detect any unusual pattern. There will be permanent contact with the main coordinator of the study and will meet face to face three times a year to evaluate the course of the study based on the data collected.

10. IMPACT ON CLINICAL PRACTICE.

Hemopatch is expected to reduce the risk of postoperative type B and C pancreatic fistula from 30% to 15%, so that the number of patients currently requiring readmission with possible surgeries and interventional radiological procedures is halved. This implies not only clinical but also economic advantages, since a pancreatic fistula can double the cost of hospital treatment.

11. ETHICS AND LEGAL REQUIREMENTS.

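### Section 7.7 withdraws patients from the study, but nothing keeps their outcomes in the primary analysis or states plainly that patients are compared as randomised

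*Combined protocol and SAP*

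**What the plan says.** **Withdrawal.** Section 7.7 opens its list with "Criteria for withdrawing a patient from the study". The list has three entries: the patient's wish, an operation not carried out because the tumour is unresectable, and "The investigator suspects a serious threat to the patient's well-being". It does not say whether outcomes already recorded are kept, whether follow-up continues, or whether these patients are analysed.

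**Follow-up and losses.** Section 6.3 says "All patients randomly assigned will be followed for 30 days after surgery, or during the total stay" if that is longer. It does not mention patients withdrawn under 7.7. Section 8.1 adds 10% for losses and does not say how lost patients are handled.

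**Grouping.** For the primary analysis, section 8.5 and the synopsis say that "patients will be dichotomized by the presence or absence of the sealant reinforcement". No analysis population (intention-to-treat, per-protocol or other) is named in the text available to this review.

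**How the arms are named elsewhere.** The synopsis describes the intervention as "Performing duct-to-mucosa anastomosis with or without Hemopatch reinforcement after PD", and section 8.2 calls the control arm "duct-to-mucosa pancreaticojejunostomy WITHOUT Hemopatch reinforcement". Sections 7.4 and 8.2 both require the operation to follow the allocation.

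**The concern.** Withdrawal in 7.7 is from the study, not only from treatment. An analyst who applies it literally drops the patient. Two of the three reasons, patient wish and investigator concern, can arise after allocation whatever the timing of randomisation.

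The third reason matters most because it is close to the endpoint itself. Section 7.6 describes grade C fistula as clinical instability with sepsis, and an investigator could well regard that as a serious threat to the patient. The rule can therefore remove patients because they are having the outcome, or are about to. If that happens unevenly between arms, the comparison loses the balance that randomisation gives.

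The grouping phrase adds a second, smaller freedom: an analyst could classify a patient by patch received and still be following the text. At the planned rates only about 10 events are expected, so the handling of a single patient can matter.

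**Working it through.** **1. The passages side by side**

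| Section | What it governs | What it leaves open |
|---|---|---|
| 7.7 | Who leaves the study | Whether their outcomes are kept or analysed |
| 6.3 | Follow-up of all randomised patients | Whether this covers 7.7 withdrawals; who is analysed |
| 8.1 | 10% allowance for losses | How losses are handled |
| 7.4, 8.2 | Operation follows allocation | What to do when it did not |
| 8.5, synopsis | Grouping by sealant present or absent | Assigned or received |

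None of these supplies an analysis rule for a withdrawn patient.

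**2. Inputs**

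- Section 8.1: 57 patients before losses; 57/(1 − 0.10) = 63.3, rounded up to 64, or 32 per arm. The allowance is 64 − 57 = 7 patients. Whether 57 follows from the stated rates is a separate question and is not used here.
- Section 8.1: fistula rates 23% (control) and 7% (Hemopatch).
- Sections 5 and 10: alternative rates of 30% and 15%.
- Assumption: the unadjusted chi-square test with Yates correction at two-sided 5% decides, in favour of Hemopatch. Section 8.5 gives both this test and a covariate-adjusted logistic model and does not say which decides.

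Expected events: 0.23 × 32 + 0.07 × 32 = 7.36 + 2.24 = 9.6.

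**3. Exact enumeration for one affected patient**

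Let x and y be the fistula counts in the control and Hemopatch arms, with binomial probabilities for n = 32. For a randomly affected Hemopatch patient:

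P(change) = Σₓ Σᵧ Bin(x; 32, p_C) · Bin(y; 32, p_H) · [(y/32)·I₁ + (1 − y/32)·I₀]

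I₁ and I₀ equal 1 if the verdict changes when the affected patient does or does not have a fistula. For a control patient, x/32 replaces y/32. In the worst case the affected patient is taken to have a fistula in every trial that has one in that arm; other trials count as unchanged.

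| Affected patient | Random, 23% v 7% | Has fistula, 23% v 7% | Random, 30% v 15% | Has fistula, 30% v 15% |
|---|---|---|---|---|
| Hemopatch, omitted | 4.2% | 14.2% | 3.8% | 8.3% |
| Control, omitted | 2.7% | 9.9% | 2.9% | 5.6% |
| Hemopatch, counted as unpatched | 5.0% | 25.1% | 5.2% | 17.2% |
| Control, counted as patched | 9.1% | 17.5% | 6.8% | 11.0% |

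The change is not mainly towards significance. At 23% v 7%, omitting a random Hemopatch patient moves 0.8% of trials to significance and 3.5% away from it. Counting that patient as unpatched moves 1.5% and 3.5%.

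**4. One table near plan, for illustration**

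χ² = N(|ad − bc| − N/2)² / (product of the four margins)

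- As randomised, 7/32 v 2/32: 64 × (160 − 32)² / (32 × 32 × 9 × 55) = 1,048,576 / 506,880 = 2.07, p = 0.150.
- One Hemopatch fistula omitted, 7/32 v 1/31: 63 × (185 − 31.5)² / (32 × 31 × 8 × 55) = 3.40, p = 0.065. The verdict is unchanged.
- The same patient counted as unpatched, 8/33 v 1/31: 64 × (215 − 32)² / (33 × 31 × 9 × 55) = 4.23, p = 0.040. The verdict changes.

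**The case against.** A reader might infer from 8.5 that an as-treated analysis is planned. The document does not support that. The arms are described throughout by the same with-or-without contrast, and section 6.1 applies it to the group to which a patient is assigned. In a two-arm randomised trial the natural meaning of the phrase is arm. The patch is also applied once, during an operation that 7.4 and 8.2 require to follow the allocation, so there is less room for crossover than with continuing treatment. This objection stands, and it makes the grouping phrase the secondary issue. It does not reach the withdrawal gap, which remains even if the phrase means arm.

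A reader might also take the move from p = 0.150 to 0.040 as the expected harm. It is not. It needs the affected patient to be one of only two fistulas among 32 Hemopatch patients, and it uses reclassification; omission, the effect tied to 7.7, leaves that table non-significant.

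Part of the sensitivity comes from the small number of events. Under the same test, power at 23% v 7% with 32 per arm is only about 30% by the same enumeration, so a result close to plan is non-significant under the as-randomised analysis anyway. That is true, but a small event count is also a reason to fix the handling of each patient in advance.

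Finally, section 6.3 can be read as keeping everyone under observation. It is a follow-up statement, is not reconciled with withdrawal from the study, and gives no analysis rule.

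Unresectable patients are a milder case. Leaving them out does no harm if resectability is settled before, or without knowledge of, allocation. Whether that holds cannot be told from the text: 7.2 starts randomisation after consent, while 8.2 places it after surgery and then has surgery follow its result.

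**Conclusion.** The concern holds as a gap with a specific route to bias. Section 7.7 removes patients for reasons that can arise after allocation, one of which overlaps with grade C fistula, and no available text keeps their outcomes in the analysis. The grouping phrase in 8.5 is a secondary ambiguity.

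At 23% v 7%, one randomly affected patient changes the verdict in about 3–4% of trials if omitted and 5–9% if counted in the other group; at 30% v 15% the figures are 3–4% and 5–7%. The worst case at 23% v 7%, where the patient has a fistula, is 10–14% and 18–25%. All of this assumes 32 per arm and that the unadjusted Yates test decides.

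These are effects per affected patient, not expected error rates. The document does not say how often withdrawals or crossovers will occur, or how many of the allowed losses would be 7.7 withdrawals. It supports neither a claim that events will be lost nor a claim that the result will be reversed. The point should be fixed, but it does not by itself invalidate the design.

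**What to change.** 1. In 8.5 and the synopsis, write: *For the primary analysis patients are compared by randomised arm, regardless of whether Hemopatch was applied.*
2. In 7.7, state that outcome data already collected on withdrawn patients are kept. Unless consent is withdrawn, these patients are followed for the primary outcome over the period already set in 6.3 (30 days, or the total stay if longer) and analysed in their randomised arm.
3. State that patients who have no pancreaticoduodenectomy may be excluded only if that is determined before, or without knowledge of, allocation.
4. As a cross-reference, reconcile the timing of randomisation in 7.2 and 8.2 so that item 3 can be applied. That contradiction is a separate matter in its own right.

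The cost is a few sentences, with no extra patients, scheduled visits or tables. The sample size of 64 is unaffected by this change. The downside is some dilution of the estimated effect if patients cross over.
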